2.9.2.1 Adverse events of special interest / grouping of AEs

The number of hospitalizations/prolongations of hospitalization due to an SAE will be summarized.

2.9.3 Laboratory data

Laboratory evaluations (hematology, chemistry, urinalysis) will be summarized by presenting summary statistics of values and change from Core baseline at applicable visits by treatment arm.

2.9.4 Other safety data

2.9.4.1 ECG and cardiac imaging data

Not applicable.

2.9.4.2 Vital signs

Vital signs (weight, head circumference, body length, standing height, knee to heel length, sitting height, leg length, and blood pressure (systolic/diastolic)) will be summarized by presenting summary statistics (n, mean, median, standard deviation, min, max, quartiles 1 and 3) for available visits by treatment group. Their changes from Core baseline values will also be summarized if applicable by treatment arm.

Leg length= standing height – sitting height

Table 2-2 Vital signs collection in Core and Extension study

Vital signs	Core study		Extension study	
Weight	x	Day 1, 85, 169	x	Year 2, 5th birthday
Head circumference	x	Day 1, 85, 169	x	Year 2
Body length*	x	Day 1, 85, 169		
Standing height*			x	Year 2, 5th birthday

Sitting height			x	Year 2, 5th birthday
Knee to heel length	x	Day 1, 85, 169		
Leg length*				
Blood pressure	x	Day 1, 85, 169	x	Year 2

Note: * body length is collected in the Core study while standing height is collected in the Extension study. These two variable are assessing whole body growth but are not fully comparable. Leg length will be derived from the standing/sitting height difference.

2.9.4.3 Health status

Respiratory function status:

The patient's respiratory function status will be summarized and listed for applicable visits by treatment arm.

For the Core study period, the requirement for respiratory support (other than oxygen therapy) and the requirement for oxygen therapy will be summarized. Positive end-expiratory pressure, fraction of inspired oxygen and percentage of oxygen saturation will be summarized by presenting summary statistics of values and change from Core baseline to day 169 by treatment arm.

For the Extension study period, the respiratory function status (wheezing/whistling status, number of attacks of wheezing, frequency of sleep disturbance, presence of wheezing limiting patient's speech ability, dry cough status and presence of smoker at home) will be summarized for the patients' 2 years' corrected age visit and 5th birthday visit.

Hearing function status:

The patient's hearing function status will be summarized and listed for the patients' 2 years' corrected age visit and 5th birthday visit.

Hospitalization:

Duration of hospitalization (from birth to first hospital discharge home) from the Core study and weight at the first discharge from hospital home will be summarized.

2.10 Pharmacokinetic endpoints

Not applicable.

2.11 PD and PK/PD analyses

[figure not shown]
Not applicable.

[figure not shown]
2.12 Patient-reported outcomes

Not reported.

2.13 Biomarkers

Not applicable.

2.15 Interim analysis

Two interim analyses will be performed by the Novartis CTT.

Interim Analysis I:

The first interim analysis will be performed when the last patient has completed the last visit in Core study or when at least half of the patients enrolled in the Core study have completed the visit corresponding to 40 weeks after the first study treatment (in the Core study), whichever is later.

The purpose of the first interim analysis is to provide some longer term data on ocular structural abnormalities. This is to comply with the plan for specific follow-up in the Pediatric Investigation Plan (EMA). At the first interim analysis, descriptive statistics will be produced as appropriate and no inferential analyses will be conducted. The variables below will be summarized.

- Epoch 1 phase subject disposition
- Subject demographics
- The absence of all ocular structural abnormalities as defined in [Section 2.8.1](#).
- The recurrence of ROP up to 40 weeks post baseline visit from the Core study
- The absence of active ROP at 40 weeks as defined in [Section 2.8.1](#)
- The number of ranibizumab injections received in the treatment of patients with ROP up to 40 weeks post baseline visit of the Core study by eye and overall
- The type, frequency, and severity of ocular and non-ocular adverse events

The above outputs will be repeated for the subgroup of Japan, to support the submission to the PMDA.

Interim analysis II:

The interim analysis II will be performed when the last patient has completed the visit which corresponds to the patient's 2 years' corrected age.

The purpose of the second interim analysis is to evaluate the absence of all ocular structural abnormalities as defined in Interim Analysis I at the patient's 2 years' corrected age.

At the second interim analysis, the variables below will be evaluated.

The appropriate CMH test (as specified in [Section 2.6.2](#)) with ROP Zone at Core baseline as stratification factor will be used to analyze secondary binary efficacy variables ([Section 2.8.1](#)) at interim analysis II. p-values and 95% confidence intervals will be provided. No adjustment for multiplicity will be conducted. For other variables, descriptive statistics will be provided by treatment arm.

Binary variables:

- The absence of all ocular structural abnormalities (as in [Section 2.8.1](#))

Other variables:

- The absence of each of the ocular structural abnormalities defined in [Section 2.8.1](#)
- The absence of active ROP at 52 weeks from the baseline visit of the Core study as defined in [Section 2.8.1](#)
- The recurrence of ROP up to 40 weeks from the baseline visit of the Core study
- The absence of active ROP, and individual components of active ROP at 40 weeks from the baseline visit of the Core study

[REDACTED]

- Patient's physical development (standing/sitting height, leg length, weight and head circumference)
- The patient's health status (respiratory function, hearing function, duration of hospitalization from birth to first hospital discharge home, and weight at discharge)
- The type, frequency, and severity of ocular and non-ocular adverse events including AEs, SAEs, AEs by maximum severity
- The type, frequency, and severity of ocular and non-ocular adverse events with onset date on/after extension baseline, including AEs, SAEs, AEs by maximum severity

[REDACTED]

- Demographics (including sex, geographical region, gestational age at birth, gestational age at birth by category) and ROP disease status by subject at core baseline will be presented descriptively.
- Summary of the safety follow-up period since Core study baseline

- Summary of body height, body weight, and head circumference at Core study baseline, at the year 2 visit of the Extension study, and their change from Core study baseline to the year 2 visit
- Subject disposition
- Summary of reasons for permanent discontinuation from study treatment
- Deaths by preferred term
- Number (%) of subjects with deaths, SAEs or AEs leading to permanent discontinuation of study treatment
- Analysis sets by treatment
- Pre-retinal fibrosis and its relationship to laser therapy, ocular injection therapy, and study drug by eye

The safety follow up period (in months) is defined as: (The earlier date of the extension EOS data and snapshot date of the interim analysis – Core study baseline date +1)/30.

In addition, a selection of the above outputs will be repeated for the subgroup of Japan, to support the submission to the PMDA.

3 Sample size calculation

The sample size calculation is not based on a power calculation. The number of patients enrolled in this study depends on the number of patients that were enrolled and completed the Core study, are willing to participate in the Extension study and fulfill the eligibility criteria of the Extension study ([Section 4](#) of Protocol).

4 Appendix

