To evaluate the absence of ocular structural abnormalities at or before 40 weeks post baseline visit in the Core study, at the patient's 2 years' corrected age and fifth birthday	
Title: absence of all ocular structural abnormalities as listed in Section 2.8.1
 
Unit of measure: number and percentage of patients
 
Time frame: at or before V203 (Week 40) in the Core/ Extension study, at or before V302 (the patient's 2 years' corrected age), at or before V399 (the patient's fifth birthday)
 
Title: absence of each ocular structural abnormality as listed in Section 2.8.1 considered individually
 
Unit of measure: number and percentage of patients
 
Time frame: at or before week 40, at or before patient's 2 years' corrected age, at or before patient's fifth birthday

To evaluate the recurrence of ROP up to 40 weeks post baseline visit in the Core study	
Title: recurrence of ROP
 
Unit of measure: number and percentage of patients with recurrence of ROP
 
Description: Recurrence of ROP is defined as ROP receiving any intervention after the 1st study treatment in the Core study^d.
 
Time frame: up to 40 weeks postbaseline visit in the Core study

To assess the number of ranibizumab injections received in the treatment of patients with ROP up to and including 40 weeks post baseline visit in the Core study	
Title: number of ranibizumab injections
 
Unit of measure: number of ranibizumab injections
 
Description: as per title
 
Time frame: up to and including 40 weeks post baseline visit in the Core study

OBJECTIVE	Endpoint Title, Description and Reporting Time frame for analysis and Unit of measure
To evaluate the refraction in each eye at the patient's 2 years' corrected age and fifth birthday ^a	
Title: refraction in each eye Unit of measure: diopters Time frame: at patient's 2 years' corrected age, patient's fifth birthday

To evaluate the physical development at the patient's 2 years' corrected age and fifth birthday ^b	
Title: standing/sitting height, leg length, weight Unit of measure: centimeter, gram (as appropriate) leg length will be derived from standing/sitting height difference Time frame: at the patient's 2 years' corrected age, at the patient's fifth birthday
 
Title: head circumference Unit of measure: centimeter Time frame: at the patient's 2 years' corrected age

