2.2 Data analysis general information

Three planned analyses will be performed in this study: two interim analyses and one final analysis at the completion of the study. The statistical analysis will be performed or directed by the Biostatistics & Pharmacometrics of Novartis.

Assessments documented in the database that occur as “bilateral” will be summarized and listed for each eye separately. To facilitate derivations and analysis based on eye, database records for bilateral will be split into two records containing identical information as the original record with the exception of the laterality which shall be recoded to “Right” and “Left”, respectively.

Change from baseline will only be summarized for patients with both baseline and post-baseline values for the relevant visit and will be calculated as:

Change from baseline = post-baseline value – baseline value

Descriptive statistics (mean, median, standard deviation, lower quartile (Q1), upper quartile (Q3), minimum, and maximum) will be presented for continuous variables. The number and percentage of patients in each category will be presented for categorical variables. If a confidence interval is presented for a categorical variable, then the exact Clopper-Pearson method ([Newcombe, R.G., 1998](#)) will be used to calculate the 2-sided 95% confidence interval.

This document is written in the future tense. It will be reviewed and updated (including conversion to past tense) for entry into the clinical study report (CSR) after the analysis has taken place. The analyses described in this document will be conducted using SAS version 9.4 or later.

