2.2.1 General definitions

Study treatment refers to study ranibizumab in both Core and Extension studies, and laser therapy in the Core study. (Please note that laser is a study treatment in the Core study but not a study treatment in the Extension study.) In this document, patient and subject are used interchangeably throughout the document.

A patient randomized to ranibizumab in the Core study can receive switch/rescue laser therapy in either eye; a patient randomized to laser therapy in the Core study can receive switch/rescue ranibizumab 0.2 mg in either eye. The change of treatment modality from laser to ranibizumab can occur at any time in the Core study and only in Epoch 1 of the Extension study, while the change of treatment modality from ranibizumab to laser can only occur in the Core study as only ranibizumab is available as study treatment in the Extension study. No further ranibizumab treatment can be administered to the eye after it has been switched to laser. The switch of study treatment occurs when the patient first receives a treatment modality other than the modality of the first study treatment in either eye, which can occur in the Core or Extension study period.

There are three treatment arms defined by the initial treatment received at baseline of the Core study:

- 0.2 mg Ranibizumab arm (same as Ranibizumab 0.2 mg arm)
- 0.1 mg Ranibizumab arm (same as Ranibizumab 0.1 mg arm)
- Laser treatment arm (same as Laser arm)

All results will be displayed by the initial treatment received at Core study baseline. If appropriate, within each of these three treatment arms, analyses may also be conducted separately for patients who received monotherapy or who switched treatment (by eye or by patient as applicable) during the Core study.

Two baselines are defined; Core baseline and Extension baseline. For statistical purposes, the last available non-missing values collected in study CRFB002H2301 or CRFB002H2301E1 prior to or on visit 201 will be considered to be the Extension baseline values. Core baseline will be used as baseline for both efficacy and safety analyses. The Extension baseline will be used for the demographic summary of the Extension study.

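### Interim analysis II asks for a change in body height from Core baseline to year 2, but the Core study records only body length and the Extension only standing height

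*SAP*

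**What the plan says.** Among the Interim analysis II outputs, SAP Section 2.15 includes a "Summary of body height, body weight, and head circumference at Core study baseline, at the year 2 visit of the Extension study". The same item then adds a change score: "and their change from Core study baseline to the year 2 visit". The change applies to all three measures, and the item carries no exception or condition for height.

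Section 2.9.4.2 lists the vital signs and when each is collected. Body height is not in that list. The note to its collection table explains that "body length is collected in the Core study while standing height is collected in the Extension study" and adds: "These two variable are assessing whole body growth but are not fully comparable". The same section makes changes from Core baseline conditional on their being applicable.

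Section 2.2 fixes the arithmetic, "Change from baseline = post-baseline value – baseline value", and limits who enters it: "Change from baseline will only be summarized for patients with both baseline and post-baseline values for the relevant visit". Section 2.2.1 fixes the reference point: "Core baseline will be used as baseline for both efficacy and safety analyses".

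The related secondary objective in Table 1-1 reads "To evaluate the physical development at the patient's 2 years' corrected age and fifth birthday". Its units are centimetres and grams, and it is defined by values at those two ages.

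**The concern.** Section 2.15 asks for a quantity that the data collection does not support. A programmer following it has to produce a height change; one following Section 2.9.4.2 may leave it out. If it is produced, the table would carry one label, body height, over two different measurements, and its change column would look like a growth estimate. Section 2.15 also says that a selection of the Interim II outputs will be repeated for the Japan subgroup to support a submission, so an ambiguous or mislabelled row could be carried into a regulatory document.

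**Working it through.** The SAP gives no figure to reproduce here. The check sets the collection table in Section 2.9.4.2 against the change rule in Section 2.2.

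**Step 1. What is measured, and when**

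| Measure | Core study | Extension | Core baseline and year 2 both available? |
|---|---|---|---|
| Weight | Day 1, 85, 169 | Year 2, fifth birthday | Yes |
| Head circumference | Day 1, 85, 169 | Year 2 | Yes |
| Body length | Day 1, 85, 169 | Not collected | No |
| Standing height | Not collected | Year 2, fifth birthday | No |

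**Step 2. Apply the change rule to each meaning of body height**

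- Standing height at both times: there is no Core baseline value. Patients without both values are left out, so n = 0.
- Body length at both times: there is no year 2 value, so again n = 0.
- Body length at Core baseline (L0) and standing height at year 2 (H2): the change is H2 − L0. This is the only reading that gives a non-empty table, and it subtracts two measures that the SAP itself says are not fully comparable.

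**Step 3. Size under the third reading**

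Let d be the amount by which body length exceeds standing height in the same child at year 2, so that length at year 2 would be H2 + d.

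- Like-for-like growth in length: (H2 + d) − L0
- Reported change: H2 − L0
- Error: (H2 − L0) − [(H2 + d) − L0] = −d

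The documents do not give d. Taking 0 to 2 cm as an assumed range, each arm's mean change is low by 0 to 2 cm.

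For arms A and B, the error in the between-arm difference in mean change is −(dA − dB), where dA and dB are the mean offsets in the two arms. If the offset does not depend on arm, dA = dB and the error is 0.

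**Step 4. What is untouched**

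By Step 1, the changes in weight and head circumference are like for like. The values at year 2 and at the fifth birthday that make up the Table 1-1 endpoint involve no subtraction from Core baseline.

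**The case against.** The SAP never writes the subtraction out; it has to be assembled from Sections 2.2, 2.2.1, 2.9.4.2 and 2.15. Section 2.9.4.2 openly acknowledges that the two measures differ and allows an inapplicable change to be omitted. The output is an extra descriptive interim summary with no test attached, and Section 2.1 says that the study's results cannot be viewed within a valid inferential context. All of this stands and limits the impact. It does not remove the conflict, because the condition in Section 2.9.4.2 is not repeated in Section 2.15, where the change is required outright.

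Three stronger readings are tempting and are not supported.

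- A reader might infer that the declared secondary outcome on physical development is compromised. Table 1-1 defines it by values at 2 years' corrected age and at the fifth birthday, not by change from Core baseline, and Section 2.15 lists physical development as a separate item without a change score.
- A reader might infer that summarising growth in centimetres and grams is itself an error. The SAP uses those units consistently, and raw units do not by themselves bias the comparison of arms. The 2-year visit is set by corrected age, which already aligns much of the age difference. The Core study was randomised; entry into the Extension could disturb the balance, but sex and gestational age are shown in the Interim II demographics. Parts of the Interim II list are also redacted, so the absence of standardised scores can be stated only for the visible text.
- A reader might infer from the visit-allocation table in Section 2.2.1.2 that timing alone could shift height by a large amount. The 2-year window runs from day 891 to day 1131 after the last menstrual period (plus the date offset in the table), which is (1131 − 891)/2 = 120 days either side of its centre. It applies only to premature-withdrawal visits, and only when the planned visit has no data. It is therefore a worst case for an individual child, not a shift in an arm mean. Turning days into centimetres also needs a growth rate that the documents do not give.

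**Conclusion.** The point holds as an internal contradiction. As written, the height component of the Section 2.15 summary cannot be produced as a like-for-like change. It is either an empty column or a difference between two measures.

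The consequence is small. It concerns one row of a descriptive interim table. The assumed 0 to 2 cm understatement per arm depends on an offset that is not in the documents, and its cancellation between arms depends on that offset being unrelated to arm. No test, primary analysis or defined endpoint is affected. The correction is still worth making, because the rule is wrong as it stands and the edit is simple.

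**What to change.** In Section 2.15, remove height from the change-from-Core-baseline summary. Replace the single body-height entry with two labelled entries: body length at Core baseline, and standing height at year 2. Keep the change for weight and head circumference. A cross-reference to the note in Section 2.9.4.2 would bring the two sections into line. The cost is a short wording change and one adjusted table shell; no new data are needed.

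Optionally, if growth from Core baseline is to be interpreted, add sex- and corrected-age-specific z-scores from a named growth standard beside the raw values, using the actual measurement dates. Sex, visit dates and gestational age are already recorded. Table 2-3 derives corrected age at Extension baseline only, so the same formula would have to be applied at the other visits. The remaining cost is choosing and naming a standard that covers the ages at which the scores are wanted. This is an enhancement, and the correction above does not depend on it.

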4.1 Imputation rules

The general approach to handling missing dates is shown below for dates of AEs, medical history diagnosis, and concomitant treatment. The imputation of missing dates for surgery or procedures will use the same rules as for concomitant treatment.

Imputation rules described here only apply to events, conditions and treatments

- (1) That are ongoing at the end of the Core study and at the time the patient enters the Extension study
- (2) That are not ongoing at the end of the Core study (start after last visit of Core study and are recorded in the Extension study for the first time).

For events, conditions and treatments that ended before/on last visit of the Core study, the imputation rules defined in the Core study are applicable.

The detailed algorithms will be described in the Programming Dataset Specifications.

For the purpose of date imputation, the treatment follow up period date is defined as the last available visit date.

4.1.1 Study drug

Missing date and time of study treatment will not be imputed for this study.

Comparison of Month section	MON MISSING	MON < TRTM	MON = TRTM	MON > TRTM
YYYY MISSING	NC	NC	NC	NC
YYYY < TRTY	01JULYYYY Before Treatment Start	15MONYYYY Before Treatment Start	15MONYYYY Before Treatment Start	15MONYYYY Before Treatment Start
YYYY = TRTY	AE start reference date + 1 day Uncertain	15MONYYYY Before Treatment Start	TRTSTD +1 Uncertain	01MONYYYY After Treatment Start
YYYY > TRTY	01JANYYYY After Treatment Start	01MONYYYY After Treatment Start	01MONYYYY After Treatment Start	01MONYYYY After Treatment Start

If the AE is not ongoing at the end of the Core study:

Comparison of Month section	MON MISSING	MON < EXTBL	MON = EXTBL	MON > EXTBL
YYYY MISSING	Uncertain	Uncertain	Uncertain	Uncertain
YYYY < EXTBL	Later of (01JULYYYY, date of last visit of Core study+1) Before Extension baseline visit	Later of (15MONYYYY, date of last visit of Core study+1) Before Extension baseline visit	Later of (15MONYYYY, date of last visit of Core study+1) Before Extension baseline visit	Later of (15MONYYYY, date of last visit of Core study+1) Before Extension baseline visit
YYYY = EXTBL	EXTBL + 1 day Uncertain	Later of (15MONYYYY, date of last visit of Core study+1) Before Extension baseline visit	EXTBL +1 Uncertain	01MONYYYY After Extension baseline visit
YYYY > EXTBL	01JANYYYY After Extension baseline visit	01MONYYYY After Extension baseline visit	01MONYYYY After Extension baseline visit	01MONYYYY After Extension baseline visit

The following table is the legend to the logic matrix.

Relationship

Before Treatment Start	Partial date indicates AE start date prior to Treatment Start Date
After Treatment Start	Partial date indicates AE start date after Treatment Start Date
Uncertain	Partial date insufficient to determine relationship of AE start date to Treatment Start Date
Before Extension Baseline Visit	Partial date indicates AE start date prior to Extension Baseline Visit Date
After Extension Baseline Visit	Partial date indicates AE start date after Extension Baseline Visit Date
Uncertain	Partial date insufficient to determine relationship of AE start date to Extension Baseline Visit Date

If a complete (imputed) AE end date is available and the imputed AE start date is greater than the (imputed) AE end date, then the imputed AE start date should be set to the (imputed) AE end date.

